#### 1. GENERAL INFORMATION

#### 1.1 Protocol full title

PneuMum: A randomised controlled trial of pneumococcal polysaccharide vaccination for Aboriginal & Torres Strait Islander mothers to protect their babies from ear disease.

### **Short Title**

PneuMum: will an injection for mothers help to protect their babies from ear disease?

# 1.4 Independent Medical Monitor

Data Safety Monitoring Board (see 12.4)

#### 2. Executive Summary

PneuMum is a randomised controlled trial that aims to find out if pneumococcal immunisation for Aboriginal and Torres Strait Islander women, in the last few months of pregnancy or at delivery, can prevent ear disease in infants.

The vaccine, called Pneumovax, is a 23 valent pneumococcal polysaccharide vaccine (23vPPV) that is recommended for all Indigenous people in the Northern Territory from 15 years of age.

# **Background and rationale**

Aboriginal and Torres Strait Islander children experience the highest rates of acute and chronic ear infections in the world, resulting in permanent ear damage, hearing loss and educational disadvantage. These infections are mainly bacterial. *Streptococcus pneumoniae* (pneumococcus) is the predominant pathogen. Pneumococcal colonisation and infection begins within days of birth, months before any potential immunological protection from infant pneumococcal conjugate vaccine may be expected. New strategies are needed to eliminate, or at least delay, this early-onset pneumococcal colonisation.

[figure not shown]
Maternal immunisation with polysaccharide pneumococcal vaccine is one strategy that may protect newborn infants through transplacental antibody transfer, increased secretory antibody in breast milk, and/or by reducing carriage (and transmission to the infant) of maternal pneumococci. Previous small studies using this strategy have been encouraging, but there have been no studies properly evaluating carriage or disease endpoints in infants.

## Methodology

The study, which has been funded by National Health and Medical Research Council, aims to recruit 210 Indigenous women aged 17-39 years who have an uncomplicated pregnancy.

Potential subjects will be contacted to seek informed consent to participate. Written and pictorial information has been developed for use with local interpreters to explain the disease, reasons for the study, and potential harms / benefits of involvement. All participants will have documentation of appropriate antenatal investigations to ensure pregnancy is proceeding normally, as far as can be determined.

Eligible subjects will be randomly assigned to one of three groups (see Box), receiving Pneumovax (23vPPV) in the last few months of pregnancy, immediately postpartum, or seven months after childbirth (the control group).

Random

Boostrix, recommended for new parents to prevent pertussis (whooping cough), will also be offered at delivery to all women who have not previously been vaccinated in accordance with NT government policy.

Although currently recommended for all Indigenous persons in the Northern Territory from 15 years of age and for others in high-risk groups, uptake of Pneumovax among women of child-bearing age has been low.

#### Outcomes

The primary outcome will be prevalence of ear infection at seven months of age, defined as middle ear effusion or tympanic membrane perforation or acute otitis media, identified by video-otoscopy and tympanometry. The primary analyses will be a direct comparison of the proportion of infants in the control group (Group 3) who have carriage of vaccine type pneumococci at seven months of age compared to infants in each of the other two groups and a similar comparison of the proportion with middle ear disease at that age.

There is a clear link between carriage of pneumococci in the first few months of life and the extraordinarily high rates of acute and chronic ear infections among Indigenous children, leading to hearing loss and educational disadvantage. Our study has the potential to demonstrate clinically significant benefits for infants in the first few months of life.

- If maternal immunisation can eliminate, or at least delay, early-onset pneumococcal colonisation it could have a substantial impact on ear disease.
- If the results of our study suggests antenatal vaccination reduces pneumococcal carriage or ear disease it would support moves to establish a much larger safety and efficacy studies of pneumococcal vaccination during pregnancy.
- If similar results are achieved from postnatal vaccination, it would provide evidence that such studies are not warranted and that the policy emphasis should be to ensure unvaccinated mothers are offered pneumococcal vaccination prior to discharge from hospital.

In addition to funding support from the National Health and Medical Research Council, the PneuMum study has been endorsed as an inkind project for the Cooperative Research Centre for Aboriginal Health and has received in-principle support from the World Health Organization and the Centre for Disease Control of the Northern Territory Department of Health and Community Services.

#### 3. Aims

### Primary aim:

• To determine if maternal immunisation with the 23-valent pneumococcal polysaccharide vaccine (23vPPV), given antepartum or immediately postpartum, can reduce pneumococcal carriage and the prevalence of middle ear disease among Indigenous children at seven months of age.

#### Secondary aims:

- To assess the acceptance of maternal immunisation in this population (as judged by the enrolment rate);
- To assess the impact against infant pneumococcal carriage and middle ear disease at one month and at two months of age;
- To assess maternal antibody response to antepartum or postpartum 23vPPV; and
- To assess the antibody response in infants of 23vPPV-immunised mothers following completion of the primary course of 7-valent pneumococcal conjugate vaccine (7vPCV).

#### 4. Rationale

Aboriginal and Torres Strait Islander children experience the highest rates of acute and chronic ear infections in the world, with resultant permanent ear damage, hearing loss and educational disadvantage. These infections are mainly bacterial, and *Streptococcus pneumoniae* (pneumococcus) is the predominant pathogen. Pneumococcal colonisation and infection begins within days of birth, months before any potential immunological protection from infant pneumococcal conjugate vaccine may be expected. New strategies are needed to eliminate, or at least delay, this early-onset pneumococcal colonisation. Maternal immunisation with 23vPPV (known as Pneumovax) is one strategy that may protect newborn infants through transplacental antibody transfer, increased secretory antibody in breast milk, and/or by reducing carriage (and transmission to the infant) of maternal pneumococci. Previous small studies using this strategy have been encouraging, but there have been no studies properly evaluating carriage or disease endpoints in infants.

[figure not shown]

## 6. Previous studies of pneumococcal vaccination in pregnancy

The data relating to pneumococcal vaccination in pregnancy have been systematically reviewed by the World Health Organization. The first trial involving pneumococcal vaccination during pregnancy was conducted in Papua New Guinea in 1973 when 187 women recruited for a larger vaccine trial were subsequently found to be pregnant after vaccination. Local custom had prevented enquiries about pregnancy at the time of recruitment so it is likely that most of the women were vaccinated early in pregnancy. Trials have now been conducted in Asia, Africa and North America involving over 800 pregnant women (Table 1).

Vaccination during pregnancy has been shown to increase maternal anti-pneumococcal IgG antibody and increase transplacental transfer to the infant through the cord blood as well as increase levels of specific antibody in breast milk. (8,10-13) The proportion of maternal anti-pneumococcal antibody transferred to the infant in these studies varied from 30% to 50% in the Gambia and Bangladesh to 89% in the USA. (8,11,13) There was also variation in the extent and duration of the antibody response for different serotypes and in different settings. Even so, the data suggest infants of vaccinated mothers have higher anti-pneumococcal antibody levels against most vaccine types during the first few months of life than infants of unvaccinated mothers with the added potential of mucosal protection through secretory IgA in the mother's milk.

The aforementioned trials focussed on vaccination during pregnancy as a source of antibody transfer to the infant and one additional study assessed the antibody response of women and infants to 23vPPV given prior to pregnancy. In each of these studies it was not possible to establish whether breast milk antibody alone could generate an adequate infant immune response in the absence of transplacental transfer. Vaccination of lactating women with 23vPPV has been shown to produce capsule-specific secretory IgA in breast milk with the potential for killing pneumococci at mucosal sites. If adequate antibody protection can be provided through breast milk, postpartum vaccination may be a preferred option for some unimmunised mothers.

## 7. Safety during pregnancy

From the trials conducted to date (Table 1), there has been no evidence of adverse events from vaccination of pregnant women with 23vPPV. (4-14) While there are no biological reasons to suspect that vaccination toward the end of pregnancy would not be safe, these trials have been too small to exclude rare, serious adverse events. The World Health Organization has acknowledged the limited data on this issue and the need for large-scale safety and efficacy studies. WHO also makes the point that smaller studies should continue to be supported where they are able to test additional hypotheses relevant to maternal pneumococcal immunisation. (4) The protocol for the PneuMum trial has been forwarded to WHO, which has provided inprinciple support for the study (see letter attached).

In Australia, national guidelines allow for 23vPPV to be given in pregnancy if the risk of pneumococcal disease is very high but otherwise recommend deferral of vaccination due to the limited data. The likelihood that administration of 23vPPV in pregnancy is safe is supported by the experience of meningococcal polysaccharide vaccines, which are similar in formulation and have been used extensively with no documented adverse events either for pregnant women or their infants. (18)

## 8. Vaccination of Aboriginal and Torres Strait Islander women

Due to high rates of invasive pneumococcal disease, the 23vPPV is recommended for all Indigenous Australians aged 15-49 years who have any high-risk underlying conditions and for other high risk groups. Within the Northern Territory, the 23vPPV is provided free for all Indigenous persons in this age group, regardless of other risk factors. However, coverage with the 23vPPV among Indigenous women of child-bearing age is estimated to be only 24% (personal communication, [name], NT DHCS).

Our study will investigate two options for maternal immunisation: antenatal 23vPPV or immediate postnatal 23vPPV. The former is not routinely recommended at present, whilst the latter, although consistent with current recommendations, is not standard practice. At present uptake of the vaccine among Indigenous women of child-bearing age has been low. Vaccination of the mothers will protect them against invasive pneumococcal disease, and could potentially have an added benefit of protecting their infants against colonisation during the first few months of life. The extraordinarily high rates of infant pneumococcal carriage and of middle ear disease among Indigenous communities in the Northern Territory provides an opportunity to assess large effects on these outcomes from a relatively small study.

A larger study than we have proposed would be able to detect smaller differences in rates of otitis media at seven months of age (if they exist), however smaller differences may be less likely to lead to changes in practice. In addition, we will be monitoring other secondary endpoints such as anti-pneumococcal antibody production. These will be useful indicators of

whether a larger study is warranted to assess the effect on less common outcomes (eg. pneumonia, invasive pneumococcal disease), more long term outcomes related to the prevention of persistent disease, ear drum perforation and hearing loss, or to evaluate smaller reductions in carriage and ear disease at the younger age points (one month and two months).

### 9. Research Plan

#### 9.1 Setting

We propose to conduct the study in Darwin and, subject to community consent, other remote communities in the Top End of the Northern Territory. By limiting recruitment and follow-up to pregnant Indigenous women from larger communities, we will maximise use of available resources within this region where there are very high rates of pneumococcal carriage and middle ear disease among Aboriginal and Torres Strait Islander infants. Another important factor is the high rate of breast feeding (84% at three months and 79% at six months). (19)

## 9.2 Study design

The study is an open label randomised controlled trial involving 210 Indigenous women aged 17-39 years who have an uncomplicated pregnancy. Once community consent is obtained, we will seek the cooperation of general practitioners in participating communities and visiting District Medical Officers to assist in the identification of pregnant women so that we Last few months can then contact them about possible of pregnancy (30-36 wks) involvement in the trial.

Following recruitment, subjects will be randomly assigned to one of three groups (see Box).

- Women in Group 1 will receive 23vPPV (Pneumovax) during the third trimester of pregnancy. We will aim to give the vaccine at 32 weeks gestation (range 30-36 weeks). As discussed later, we have opted not to use an alternative vaccine at this time point for the other groups.
- Women in Group 2 will receive 23vPPV (Pneumovax) at delivery.
- Women in Group 3 will be offered 23vPPV when their infant is aged at 7 months (the end of the observation period).

Random allocation Group 1 Group 2 Group 3 Given to Mother baby is born Baby still gets all the vaccines normally recommended at 2, 4 and 6 months Offered to Mother when the baby is

All women will be offered adult diphtheria, tetanus and acellular pertussis vaccine (Boostrix) at delivery in accordance with NT government policy. Those women who had not received Boostrix by the time of the 7 month visit will again be offered the vaccine at that time. The provision of *Boostrix* for mothers soon after delivery is consistent with the recommendations of the Australian Immunisation Handbook and is now an NT government funded program to minimise the risk of transmission of pertussis (whooping cough) from the parent to the newborn infant.

when the

7 months

#### 9.3 Primary and secondary analyses

The primary outcome will be prevalence of ear infection at seven months of age defined as middle ear effusion or tympanic membrane perforation or acute otitis media identified by video-otoscopy and tympanometry. Seven months was chosen as the age to assess the primary outcome because both carriage and middle ear disease are well established by this age and the child's language development may be at risk from the associated hearing loss. Further, all children should have received their primary course of 7vPCV by this age. Thus assessment at seven months will provide the best opportunity to identify an additional impact of each maternal immunisation strategy on pneumococcal carriage and ear disease in children.

Analysis will be performed on an intention-to-treat basis, with a secondary per-protocol analysis performed as well. The primary analyses will be a direct comparison of the proportion of infants in the control group who have carriage of vaccine type pneumococci at seven months of age compared to infants in each of the other two groups and a similar comparison of the proportion with middle ear disease at that age. We used recent unpublished data from a longitudinal study in the NT to calculate baseline rates (Table 2) since these rates were lower than those of previously published data. We aim to recruit 70 evaluable subjects per group, which will be sufficient to demonstrate a 45% reduction in pneumococcal carriage or a 23% reduction in middle ear disease at seven months of age. In the event that maternal immunisation in the third trimester is effective, a difference of this size would mean that five pregnant women would need to be immunised to prevent one child from having otitis media at seven months of age. Given the uncertainty surrounding the use of vaccines during pregnancy, we believe differences smaller than this may be unlikely to change practice.

Table 2 Sample size estimates per group for primary and secondary endpoints

Endpoint	Infant	Control group	Vaccine group	Sample
-	Age		(reduction)	size
Nasopharygeal carriage of	7 months	55%	30% (-45%)	68
pneumococci serotypes contained in	2 months	39%	16% (-59%)	67
the 23vPPV	1 month	20%	3% (-85%)	66
Middle ear effusion or acute otitis	7 months	90%	69% (-23%)	66
media or tympanic membrane	2 months	70%	45% (-36%)	68
perforation	1 month	44%	20% (-55%)	67

The true immune correlate for protection from pneumococcal disease is not known. Based on experience with the comparable Hib vaccines, data from animal models and the limited efficacy data available, regulatory agencies now believe that anti-capsular antibody levels represent the best guide to immunity following vaccination. While the actual protective level probably varies with serotype and disease manifestation, antibody levels greater than 0.35 mcg/ml are expected to indicate protection against invasive disease. We will conduct a chi-squared analysis to determine the effects of the vaccine on the proportion of mothers with anti-capsular pneumococcal antibodies greater than 0.35 mcg/ml at delivery and the proportion of infants with anti-capsular pneumococcal antibodies greater than 0.35 mcg/ml at seven months of age.

## 9.4 Eligibility for recruitment

Subject to community consent, all women of Aboriginal and/or Torres Strait Islander descent aged 17 to 39 years who have a singleton uncomplicated pregnancy and reside in Darwin or participating communities will be eligible for recruitment in the trial provided that:

- the subject intends to deliver her child at the Royal Darwin Hospital or Darwin Private Hospital and
- has given informed consent to participate.

A complicated pregnancy is defined as an existing pregnancy complication (eg significant pre-eclampsia with hypertension, proteinuria and oedema) or any pre-existing condition judged by the clinical investigator to make pregnancy high-risk. Eligibility will be confirmed after the routine antenatal at 28 weeks to ensure that the pregnancy is proceeding normally. Subjects will be excluded if they:

- have had 23vPPV (Pneumovax) within the previous three years;
- intend to leave the study area during the follow-up period;
- are HIV positive, have a history of severe allergy, uncontrolled asthma or splenectomy.

A record will be kept of the reasons for exclusion.

#### 9.5 Enrolment and consent

Consistent with our previous clinical trials involving Indigenous communities, we will first obtain community consent before approaching any individuals. Community meetings will be conducted to explain the trial objectives, the potential risks and benefits associated with involvement. These meetings will be conducted with community groups such as women's centres, Councils and health clinic staff, providing written and pictorial information, translated as appropriate.

Once community consent is obtained, we will seek the cooperation of general practitioners in participating communities and visiting District Medical Officers to identify pregnant women of Aboriginal and/or Torres Strait Islander descent so that they and their families can then be contacted by members of the project team about possible involvement in the trial. All participants will have documentation of appropriate antenatal investigations to ensure pregnancy is proceeding normally, as far as can be determined. We will provide a participant information package that explains the disease, reasons for the study, and potential harms/benefits of the study protocol. This will be in line with a previous informed consent package that we developed and piloted for a proposed effectiveness trial in NT Aboriginal communities of an unlicensed pneumococcal conjugate vaccine. (21) Written informed consent will be obtained from all participants.

#### 9.6 Randomisation and vaccination

Subjects will be randomised to one of three groups:

- (1) antepartum 23vPPV (given during the 3rd trimester)
- (2) postpartum 23vPPV (given immediately following delivery)
- (3) control group (23vPPV given seven months after delivery).

The allocation of subjects to each group will occur following enrolment and be conducted by a person independent of the study. Allocation will be stratified by the urban or remote nature of the participant's community of residence and concealed using sequentially numbered opaque sealed envelopes. The random allocation sequence will be computer generated by the Menzies School of Health Research statistician who will be independent of the study.

The conjugate vaccine (7PCV) was not considered a viable alternative to 23vPPV because of limited serotype coverage when used alone and the likelihood of increased reactogenicity if combined with a polysaccharide booster in the third trimester. We considered including a saline placebo during the third trimester for groups 2 and 3 but did not proceed with this design due to concerns about the acceptability of a placebo during pregnancy.

All laboratory assessments will be undertaken without knowledge of the subject's vaccination status and all the results of all video-otoscopy recorded during the field visits will be reviewed by an independent investigator blinded to the subject's vaccination status.

The vaccines will be given by an approved immunisation provider as an intramuscular injection to the upper outer arm using sterile technique. Subjects will be observed for up to one hour after vaccination with resuscitation equipment available and a physician in attendance. An adverse events form (including any abnormal pregnancy events) will be placed in the medical records of participants for completion by health staff. For those women vaccinated in pregnancy, a project team member will reassess the study participant at 1-3 days post-vaccine and will review hospital admissions for the period 7 days post-vaccination in order to confirm no potentially serious adverse events (SAEs) have occurred. An independent Data Safety Monitoring Board (DSMB) will be established to assess safety of the trial and to safeguard the interests of trial participants (see Section 8). The DSMB will be informed within 24 hours of receipt of a SAE.

Subjects with severe acute illness at the time of presentation will not be vaccinated. Following the conclusion of the observation period, seven months after childbirth, those subjects who have not received 23vPPV or dTpa (Boostrix) will be offered the vaccine. All subjects will be advised about other vaccines that they are recommended to receive in future.

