### 9.7 Follow-up and specimen collection

Each participant and newborn child will followed-up by a member of the study team at birth, one, two and seven months after birth (Figure 2). Infant MEE, AOM and TMP will be assessed using video-otoscopy and typanometry at age one, two and seven months. At their first assessment, infants will also receive a full '6 week' postnatal clinical examination. Infants will also have their nutritional, respiratory, and skin status assessed and treated in accordance with current standard treatment guidelines at every assessment. All assessments will be conducted by a clinician trained in the effective management of common medical problems of infants in remote communities. These examinations and interventions are likely to mean that all children participating in the study will benefit from additional medical care. Parent interview and medical record review will be used to record all potential factors that could affect acquisition of the pneumococcus in mother and baby (including number of siblings, antibiotic usage, housing, nutritional status, and smoking exposure status).

Maternal specimens will be collected immediately prior to vaccination (to determine baseline anti-capsular pneumococcal antibodies); at delivery (cord blood, serology, nasopharyngeal swab, breast milk); and at one month (breast milk), two months (repeat serology and breast milk) and seven months after childbirth (breast milk). Infant nasopharyngeal swabs will be collected at one, two and seven months with a follow-up serology at seven months (one month following completion of the primary course of 7vPCV).

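### Masked reading is planned for the video-otoscopy but not for the tympanogram or the combined ear diagnosis, which leaves a risk of assessment bias in the primary ear outcome

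*Protocol*

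**What the plan says.** Protocol section 9.3 sets the primary outcome as ear infection at seven months, "defined as middle ear effusion or tympanic membrane perforation or acute otitis media identified by video-otoscopy and tympanometry". The Executive Summary gives the same definition. Both instruments therefore contribute to the endpoint.

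Section 9.2 states: "The study is an open label randomised controlled trial". Section 9.6 records that a third-trimester placebo was rejected: "We considered including a saline placebo during the third trimester for groups 2 and 3 but did not proceed with this design".

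Masked assessment appears in one sentence of section 9.6 and covers two things:

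- **Laboratory work:** "All laboratory assessments will be undertaken without knowledge of" vaccination status.
- **Recorded video:** the "results of all video-otoscopy recorded during the field visits will be reviewed by an independent investigator blinded" to vaccination status.

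Section 9.7 has effusion, acute otitis media and perforation assessed with both instruments at one, two and seven months, and adds: "All assessments will be conducted by a clinician trained in the effective management of common medical problems of infants in remote communities". It does not say whether this clinician is masked.

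**The concern.** The protocol recognises observer bias in an open-label trial and guards against it for one of the two instruments that define the ear outcome. For the other instrument, and for the step that turns the two results into a single diagnosis, it gives no safeguard. The visit will also produce two ear classifications, one from the field clinician and one from the blinded video review. The protocol does not say which is analysed or what happens when they differ.

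With no placebo, classification of the endpoint is a direct route by which knowledge of allocation could affect the result. A tympanogram leaves some room for judgement: whether to repeat the test, whether to accept a trace, how to class it, and how to weigh it against the otoscopy. If those choices leaned even slightly towards fewer positives in a vaccine arm, the result would look like the effect the trial seeks. The expected prevalence is high and each arm has only 70 infants, so a few reclassified infants matter.

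**Working it through.** **1. What is masked, element by element**

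| Element | Masked in the protocol? | Where |
|---|---|---|
| Nasopharyngeal carriage (laboratory) | Yes | 9.6 |
| Review of recorded video-otoscopy | Yes | 9.6 |
| Performing and classifying tympanometry | Not stated | 9.6 and 9.7 are silent |
| Combined ear diagnosis | Not stated | 9.3, 9.6 and 9.7 are silent |
| Which ear classification is analysed | Not stated | 9.3 and 9.6 are silent |

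**2. The plan's own figure**

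Table 2 in section 9.3 gives 66 per group for ear disease at seven months: 90% against 69%, 80% power, two-sided alpha 0.05.

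- Without continuity correction, the pooled proportion is (0.90 + 0.69)/2 = 0.795. Then n0 = [1.96 x sqrt(2 x 0.795 x 0.205) + 0.842 x sqrt(0.90 x 0.10 + 0.69 x 0.31)]^2 / 0.21^2 = (1.119 + 0.464)^2 / 0.0441 = 56.8, so 57.
- With continuity correction, n = (n0/4) x [1 + sqrt(1 + 4/(n0 x 0.21))]^2 = 66.0, so 66.

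The stated 66 is reproduced, and all six rows of Table 2 reproduce with the correction. None of these figures is in dispute. They matter here because they imply a continuity-corrected test, while the text of 9.3 says only chi-squared. Both versions are therefore shown below.

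**3. Illustration of how much misclassification would matter**

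Inputs from section 9.3: 90% prevalence, 70 evaluable infants per group, two-sided 5% test. Assumptions not in the documents: no true effect, and a fraction m of all true positives in one vaccine arm recorded as negative. Recorded prevalence is then 0.90 in controls and 0.90 x (1 - m) in the vaccine arm.

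The chance of a falsely significant benefit is the sum, over all pairs with x > y and chi-squared above 3.84, of Bin(x; 70, 0.90) x Bin(y; 70, 0.90(1 - m)). Here x and y are the positives in the control and vaccine arms, and

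chi-squared = 140 x (70|x - y| - c)^2 / [70 x 70 x (x + y) x (140 - x - y)],

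with c = 0 uncorrected and c = 70 with continuity correction (the bracket is set to zero if negative).

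| m | Expected infants under-called (63 x m) | Recorded prevalence, vaccine arm | False benefit, uncorrected | False benefit, corrected |
|---|---|---|---|---|
| 0 | 0 | 90.0% | 2.6% | 1.3% |
| 1% | 0.6 | 89.1% | 3.7% | 2.0% |
| 2% | 1.3 | 88.2% | 5.2% | 3.0% |
| 5% | 3.2 | 85.5% | 12.3% | 8.1% |
| 10% | 6.3 | 81.0% | 32.6% | 24.8% |

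The 63 is 70 x 0.90.

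**4. Which rows are plausible**

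The table applies m to every positive infant. If the blinded video reading decides its own part of the endpoint, only positives that rest on the tympanogram are exposed. Write s for that share and u for the under-calling rate among them, so that m = s x u. The documents give neither. If, purely as an assumption, s = 20% and u = 10%, then m = 2%. Reaching m = 10% at s = 20% would need u = 50%. The lower rows are easier to reach, and the 5% and 10% rows are upper-end scenarios.

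**The case against.** Several counter-arguments have weight.

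- **Knowledge of allocation is inferred.** A reader might infer that the field clinicians are unblinded. The protocol does not say so. Open label does not by itself mean that assessors know the group, and section 9.6 has the vaccine given by an approved immunisation provider. The seven-month vaccine offer to control mothers could reveal allocation, but sections 9.2 and 9.6 place it at or after the end of the observation period. This stands: the inference is reasonable, because no assessor masking is stated, but it remains an inference.
- **Tympanometry is an instrument reading.** This stands in part. It narrows the scope for bias to test performance, acceptance and classification of traces, and their combination with otoscopy.
- **The blinded video review is probably meant to feed the outcome.** This is plausible, and nothing says that the field diagnosis is analysed. A reader might also infer that a tympanogram alone can set the outcome, or override the video. The documents do not say that either. The text leaves both questions open.
- **These are details for the statistical analysis plan, which is not shown.** This holds for the combination rule and for naming the reading to be analysed. It does not hold for masking. If de-identified traces are not kept at the visit, no later plan can supply a blinded reading of them.
- **The carriage comparison is untouched.** This is correct. Section 9.3 names it among the primary analyses, and its laboratory work is masked.

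**Conclusion.** The gap is real but limited. One of the two instruments behind the primary ear outcome, and the combined ear diagnosis, have no masking provision in an open-label trial without placebo. The protocol also does not say that the blinded reading is the one analysed.

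This is a risk of assessment bias. The documents do not show that bias will occur, and they do not support the stronger reading that the whole ear endpoint is unmasked or that unblinded clinicians decide it.

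The size depends on under-calling rates that the documents do not give. At 1% to 2% of all vaccine-arm positives, the chance of a false benefit is 3.7% to 5.2% uncorrected (2.0% to 3.0% with continuity correction). At 5% to 10% it is 12% to 33% (8% to 25%). The starting points with no under-calling are 2.6% and 1.3%. These results assume no true effect, 90% true prevalence, 70 infants per arm and misclassification in one direction in one arm only. The larger rates are upper-end scenarios, because only positives resting on the tympanogram are exposed.

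The change should be made: it is cheap, and it has to be in place before the visits.

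**What to change.** In Protocol sections 9.3 and 9.6, state that:

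1. tympanograms are stored, de-identified and sent with the videos to the blinded reviewer already planned;
2. this reviewer classifies effusion, perforation and acute otitis media from both sources by fixed, written criteria, including how the two are combined;
3. this combined blinded classification is the primary ear outcome;
4. the field diagnosis is used only for care and for a sensitivity analysis.

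The cost is storing and forwarding the traces and slightly more reading time. No visit, procedure or staff member is added, and clinical management does not change.
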